## 4. AMENDMENTS AND UPDATES

None.

## 5. MILESTONES

Milestone	Planned date
Start of data collection	April 2020
End of data collection	June 2030
Registration in the EU PAS register	01 March 2020
Interim study reports	April 2021, April 2022, April 2023, April 2024, April 2025, April 2026, April 2027, April 2028, April 2029, April 2030
Final study report	December 2030

## 6. RATIONALE AND BACKGROUND

VYNDAQEL® (tafamidis meglumine 20 mg capsule) once daily was first approved in the EU for transthyretin amyloid polyneuropathy (ATTR-PN), also known as transthyretin familial amyloid polyneuropathy (TTR-FAP) under exceptional circumstances on 16 November 2011. The product has been approved for ATTR-PN in over 40 other countries since then. TESPO, a worldwide approach to enhanced surveillance of pregnancy and birth outcomes in women with ATTR-PN exposed to tafamidis, was implemented as an additional pharmacovigilance activity in the EU Risk Minimization Plan (RMP), classified as a category 3 post-authorization measure (PAM), and has been in effect since 2011. As of 25 September 2019, there were 20 cases of exposure in utero to tafamidis, of which 13 were maternal exposure, during or within 1 month prior to pregnancy in the overall tafamidis program (clinical and non-interventional studies: Fx-005 (1); Fx1A-303 (2); Transthyretin Amyloidosis Outcomes Survey [THAOS](17).

On 03 May 2019, with the US approval of VYNDAQEL® once daily at a dose of 80 mg (tafamidis meglumine 4 x 20 mg capsules), and VYNDAMAX® (tafamidis 61 mg capsule) once daily for transthyretin amyloid cardiomyopathy (ATTR-CM), FDA required a post-marketing requirement (PMR 3576-1). To meet this post-marketing requirement (PMR 3576-1), this study will describe birth outcome frequency within the reported pregnancies in women with ATTR exposed to tafamidis during or within 1 month prior to pregnancy that are collected using the ongoing TESPO surveillance program and/or standard EDP and follow-up information collected in interventional studies.

In addition to US approval, tafamidis for the treatment of patients with ATTR-CM has been approved in Japan, United Arab Emirates, Brazil Canada, European Union, Singapore, Switzerland and Australia at this time.

This descriptive non-interventional study is designated as a Post-Authorization Safety Study (PASS) and is a commitment to the US FDA.

## 6.1. Disease Background

Transthyretin amyloidosis (ATTR) is a rare protein misfolding disease with a broad spectrum of manifestations. The condition is caused by the destabilization and dissociation of the native TTR tetramer which can result in misfolding and the formation of amyloid fibrils and progressive amyloid deposition in tissues. This can occur in amounts sufficient to impair normal functioning. The 2 major phenotypes which form the spectrum of ATTR are ATTR-PN, also referred to as TTR-FAP, which primarily affects the peripheral and autonomic nerves, and ATTR-CM which primarily affects the myocardium. These clinical manifestations may occur in isolation or together. Both result in progressively impaired function, and ultimately in death. ATTR is both a hereditary as well as an age-related disease. More than 120 TTR single site variants have been identified and associated with ATTR.

ATTR-PN is a late onset, autosomal dominant disease characterized by inexorable neurodegeneration associated with sensory loss, motor weakness and autonomic dysfunction such as dizziness, gastrointestinal disorders, sexual dysfunction and urinary incontinence. The most common variant associated with polyneuropathy is valine replaced by methionine at position 30 (Val30Met) accounting for approximately 85% of patients worldwide. Males and females are similarly affected. ATTR-PN disease usually begins in the third or fourth decade, but the onset of symptoms may be later. Age of onset ranges from mid-30s in the endemic areas of Portugal and Japan to the late 50s/early 60s in Sweden and the United States. After a mean interval of 10 years from initial symptom, patients usually die from progressive and relentless worsening of the neuropathy, secondary infections, cachexia or sudden death.

ATTR-CM is associated with both wild-type and genetic variants of TTR such as valine replaced by isoleucine at position 122 (Val122Ile) and leucine replaced by methionine at position 111 (Leu111Met). The Val122Ile mutation allele occurs in 3.3% to 4.0% of the US African-American population, and is exceedingly rare in White patients. ATTR-CM is currently associated with mean progression to death within 2 to 3 years (median survival 25.6 months) of diagnosis for variants and up to 5 years (median survival 43.0 months) for wild type, with most patients dying from cardiac causes, including sudden death, congestive heart failure, and myocardial infarction.

In wild-type disease, TTR may become structurally unstable and result in deposition of amyloid fibrils, primarily in heart tissue, and will ultimately lead to diastolic dysfunction, restrictive cardiomyopathy and heart failure. The frequency of TTR amyloid deposition

in cardiac ventricles reported from autopsy studies in patients >80 years of age range from  $1.8\%^3$  to 16.5%, with a rate of clinical cardiac disease premortem of 34%.

ATTR-CM typically occurs in patients aged 60 years or older, though the Leu111Met variant may express ATTR-CM in patients at an earlier age. ATTR-CM (both wild type and variant TTR) uniformly presents with the typical symptoms of heart failure (restrictive cardiac disease), including shortness of breath, dyspnea on exertion, orthostatic hypotension, syncope and dysrhythmias including atrial fibrillation. Signs of ATTR-CM are assessed via tests performed as part of routine heart failure assessment making the diagnosis of cardiac amyloidosis difficult, resulting in diagnosis delays, and under diagnosis of ATTR-CM. The prevalence of ATTR-CM is defined as rare, but no prevalence estimates have been published. Though prevalence of wild-type ATTR-CM is uncertain, studies using a non-biopsy approach to diagnosis, report a prevalence of 13% in heart failure patients with preserved ejection fraction, 16% in patients undergoing transcatheter aortic valve replacement for severe aortic stenosis, and 5% of ATTR-CM is associated with genetic variants of TTR such as Val122IIe and Leu111Met.

Of note, due to the typical age range for ATTR-CM patients ( $\geq 60$  y.o.) the expected number of exposure during pregnancy is anticipated to be very low, due to the low number of women of child-bearing potential in this population.

## 6.2. Tafamidis

## 6.2.1. Mechanism of Action

Tafamidis is a selective stabilizer of tetrameric wild-type TTR and of amyloidogenic variants of TTR, of which Val30Met mutation (primarily affecting the peripheral nerves) and Val122Ile mutation (primarily affecting myocardium) are the most abundant. Mixed phenotypic presentations (ie, polyneuropathy and cardiomyopathy) are frequent in non-Val30Met TTR mutations. The underlying mechanism of TTR amyloid disease, regardless of the phenotypic presentation is believed to be an accelerated deposition of the unstable TTR monomers.

Tafamidis binds to the native tetrameric forms of TTR and thereby inhibits tetramer dissociation, the rate limiting step in the formation of TTR amyloid. Tafamidis has an approximate 55-hour half-life and has been demonstrated to achieve stabilization of the TTR tetramer in over 40 mutations and wild-type TTR, for which it was tested. This novel class of TTR stabilizing drug disrupts the progression of ATTR.

## 6.2.2. Relevant Nonclinical Findings

There was no evidence of adverse effects of tafamidis on fertility, or reproductive performance, or mating behavior in rats. In animal reproductive studies, oral administration of tafamidis meglumine to pregnant rabbits during organogenesis resulted in adverse effects on development (embryofetal mortality, fetal body weight reduction and fetal malformation) at a dose providing approximately 9 times the human exposure area under the curve (AUC) at the maximum recommended human dose (MRHD), and increased incidence of fetal skeletal variations at a dose providing equivalent human exposure (AUC) at the MRHD. Postnatal mortality, delayed male sexual maturation, and impaired learning and memory were observed in offspring of pregnant rats administered tafamidis meglumine during gestation and lactation at a dose approximately 2 times the MRHD based on body surface area (mg/m^2).

Nonclinical studies with tafamidis indicate that there are no effects on the male germ cell before conception. In toxicology studies there was no evidence of genotoxicity, no histopathological changes in testis or epididymis and no effects on male fertility at doses up to 30 mg/kg. Therefore, the risk for male-mediated developmental toxicity is considered to be low because the levels of tafamidis estimated to be transferred in semen are significantly lower than the concentrations that cause developmental toxicity in nonclinical studies.

In summary, anomalies have been observed in rabbit and rat reproductive toxicology studies. In humans, ATTR could present during the patient's reproductive years, although based on our current understanding of age of onset of disease, this is more likely for a patient with ATTR-PN rather than ATTR-CM. On account of the low prevalence of ATTR-PN and ATTR-CM (rare diseases), limited reproductive data are available in humans. There has been a low incidence of exposures reported in women with ATTR-PN in the ongoing TESPO surveillance program from clinical and NI studies over a 7-year period. Nonetheless, given that tafamidis meglumine/tafamidis may cause fetal harm, product labeling recommends avoidance of pregnancy in female patients receiving tafamidis; breastfeeding is also not recommended during treatment with tafamidis. B3461091 will collect and summarize data on pregnancy outcome and birth outcome in women with ATTR exposed to tafamidis during or within 1 month prior to pregnancy.

## 7. RESEARCH QUESTION AND OBJECTIVES

This global, prospective, non-interventional study of women diagnosed with ATTR exposed to tafamidis during and 1 month prior to pregnancy is intended to summarize and report pregnancy and birth outcomes and potential adverse effects on the developing fetus and neonate.

The specific objectives are:

- 1. Describe birth outcome frequency within the reported pregnancies (live full term or premature birth, spontaneous or induced abortion, and stillbirth) in women with ATTR exposed to tafamidis during or within 1 month prior to pregnancy.
- 2. Describe the frequency of reported fetal, neonate and infant outcomes within the reported pregnancies (major congenital malformations/anomalies [overall and specific]), low birth weight, SGA, preterm birth, low Apgar score at 1 and 5 minutes, and infant milestone status at 6 and 12 months) following tafamidis exposure in women with ATTR during or within 1 month prior to pregnancy.

## 8. RESEARCH METHODS

## 8.1. Study Design

This is a global, prospective, non-interventional study designed to collect information on pregnancy outcomes in women with ATTR exposed to tafamidis during or who became pregnant within 1 month after discontinuation of drug.

[figure not shown]
This PMR study (B3461091), which is anticipated to start in 2020 and complete in 2030 will utilize routine pharmacovigilance activities in addition to the data collection and process implemented via the ongoing Tafamdis Enhanced Surveillance for Pregnancy Outcomes (TESPO) program, which will be maintained at least until 2030. Time of enrollment is the time of initial awareness of the pregnancy reported by an investigator (clinical trial) or the HCP or patient (non-clinical source). Once initiated, all prospective pregnancy events captured via Study B3461091 (including new data collected in TESPO) will be reported to regulatory agencies in aggregate reports via Study B3461091.

TESPO is descriptive, non-interventional, observational program which has been ongoing since 2011 as an EMA post marketing requirement to assess outcome of pregnancy and birth outcomes (including major birth defects and/or developmental abnormalities in live born children up to 12 months) in female patients with ATTR-PN with exposure to tafamidis during or within 1 month prior to the pregnancy. All TESPO data are collected through use of the standard pharmacovigilance EDP form and follow-up form and the Tafamidis Enhanced Surveillance data capture aid (DCA) and 12-month follow up forms. Collection of data will be updated to include ATTR-CM. Updates will also include maternal assessment at mid-point during pregnancy and 6 month assessment of infant in addition to timepoints already collected. This collection will be achieved by adding a non-standard data collection time point (triggered at 2nd trimester of gestation) and at 6 months post delivery using the standard EDP Follow-Up Form. The data are stored in the Pfizer safety database (ARGUS) and reported with routine pharmacovigilance activities. Below is a schematic of the TESPO study design (Figure 1).

Figure 1. Study Population Flow Diagram

- Women exposed to tafamidis meghumine/tafamidis during pregnancy or who became pregnant within 1 month after discontinuation of drug
- During the data collection period of April 2020 June 2030
- No exclusions

PFIZER CONFIDENTIAL CT24-WI-GL02-RF02 1.0 Non-Interventional Study Protocol Template For Secondary Data Collection Study 15-Aug-2018 Page 17 of 42

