## 8.3. Variables

Variables to be evaluated in this study include patient medical/obstetrical history and pregnancy status and outcomes, neonate and infant development status at birth, and at 6 and 12 months of age.

Variable	Description	Data Source
Maternal status		
Obstetrical History Number of pregnancies Outcome of previous pregnancies	Number of pregnancies including current pregnancy Outcomes of previous pregnancies (full term/premature live birth, stillbirth, etc) Number of living children, children born with congenital anomalies History of infertility	EDP form
Date of first day of last menstrual period	DD-MMM-YYYY	EDP form
Estimated date of conception	DD-MMM-YYYY	EDP form
Tafamidis Exposure	Formulation and dosage. Start and stop dates of tafamidis	EDP form
Exposure to concomitant medications that have risk of congenital abnormalities	Dose and start and stop dates of these concomitant medications	EDP form
Gestational age at exposure	Gestational age of fetus at exposure to tafamidis or other medication (weeks or trimester)	EDP form

PFIZER CONFIDENTIAL

CT24-WI-GL02-RF02 1.0 Non-Interventional Study Protocol Template For Secondary Data Collection Study 15-Aug-2018 Page 19 of 42

Variable	Description	Data Source
Medical History Risk Factors	Risk factors for adverse pregnancy outcomes (ie, environmental exposures, eg, hypertension, diabetes, etc.	EDP form
	Family history of congenital abnormality/genetic diseases	
Smoking	Type and number per day	EDP form
Alcohol use	Type and frequency	EDP form
Illicit drug use	Type and frequency	EDP form
Current Pregnancy		,
Maternal assessment at time of study enrollment	Vital Signs BP, temp, pulse	
Smoking during pregnancy	Type and number per day	EDP form
Alcohol use during pregnancy	Type and frequency	EDP form
Illicit drug use during pregnancy	Type and frequency	EDP form
Other relevant medical conditions, use of concomitant medications, other exposures to drugs	Comorbities/hospitalizations during pregnancy/other concomitant medications or treatments taken during pregnancy	EDP form
Maternal assessment during 2 nd trimester	Vital Signs BP, temp, pulse	EDP form

Variable	Variable Description			
Smoking during pregnancy	Type and number per day	EDP form		
Alcohol use during pregnancy	Type and frequency	EDP form		

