## 8.6. Data Management

# 8.6.1. Case Report Forms (CRFs)/Data Collection Tools (DCTs)/Electronic Data Record Process for Enhanced Surveillance

As used in this protocol, the term CRF[/DCT] should be understood to refer to either a paper form or an electronic data record or both, depending on the data collection method used in this study. For this study the data collection forms are considered the CRF.

Reported neonate and infant adverse events associated to EDPs in women exposed to tafamidis will be entered by the Pfizer Data Safety Unit (DSU) as a separate adverse event from the EDP case (cases will be linked) in the safety database. These infant adverse event cases will then be followed-up via the standard process (Table 2) used for all safety reports in order to obtain all available information. This process applies to both clinical and spontaneous EDP reports.

Case Type	1 st Follow-Up Attempt	2 nd Follow-Up Attempt	Minimum Requirements
Clinical Studies	Within 10 calendar days for SRD 	20 calendar days after 1 st f/u  attempt	
 
For Pfizer-sponsored clinical studies: 2 f/u attempts and:
 
If contact with site is established, continue until all f/u information is obtained.
 
If no response from site after 2 attempts, escalate with standard "Follow-up Escalation Notice" to obtain information.
 
For non-Pfizer-sponsored clinical studies: 2 f/u attempts and case closed as per standard Pfizer DSU procedure.
 

Non-Clinical Sources:	Within 10 calendar days for SRD	20 calendar days after 1 st f/u attempt	Two follow-up attempts and case closed as per standard Pfizer DSU procedure.

Table 2.	Timelines for Follow-Up Requests and Additional Follow-up Attempts
----------	--

: SRD: Safety Receipt Date; : f/u: follow-up; : DSU: Drug Safety Unit. Source: Pfizer internal Standard Operating Procedures.

For clinical EDP cases with associated neonate and infant adverse events, the investigator is responsible for securing patient consent and collecting detailed information. For post-marketing cases the patient reporting the infant adverse event, and the patient HCP if consented by the patient, will be responsible for providing detailed information. Data on infant adverse events may be collected via three avenues: the EDP Follow-Up Form, the TESPO Form and the separate infant case process.

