## 8.7. Data Analysis

Given the expected low number of reported pregnancy exposures, no formal data analysis or hypothesis testing will be conducted. Data collected on exposures and outcomes will be summarized descriptively. Summaries of the numbers of pregnancies and incidence proportion (percent) of adverse pregnancy and birth events reported via TESPO and/or captured in the standard EDP or SAE form entered into ARGUS will be provided. Women with ATTR exposed during pregnancy to concomitant medications with a known increased risk for congenital anomalies will be excluded from the descriptive summary but will be included in the study and described separately.

There are no known epidemiologic data on the incidence of adverse pregnancy outcomes in the ATTR population. Therefore, epidemiologic data on the incidence of adverse pregnancy outcomes in other populations (eg, the general population, particularly in those regions where tafamidis is commercially available and tafamidis unexposed pregnancies reported in THAOS) may be used to contextualize the findings.

A separate descriptive summary based on prospective and retrospective cases will be performed and submitted to the Agency. Prospective cases are defined as women who enroll prior to the occurrence of the pregnancy outcome (live birth, miscarriage, stillbirth, pregnancy termination). Retrospective cases are defined as women who enroll or contact the registry after the pregnancy outcome has occurred (live birth, miscarriage, stillbirth, pregnancy termination). Stratified analysis of the reported pregnancy outcomes, including pregnancies in women reported prior to start of this protocol, will be performed by daily maternal dose.

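### In the prospective summary, entry at any gestational age biases the crude miscarriage percentage low, and the prospective label admits pregnancies already known to be abnormal

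*Protocol*

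**What the plan says.** The protocol fixes four things that act together.

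- **Entry.** Section 8.1: "Time of enrollment is the time of initial awareness of the pregnancy reported by an investigator" for trial cases, or by the health care professional or patient for other sources. No gestational-age limit is set, and 8.2.2 has no exclusions.
- **Classification.** Section 8.7: "Prospective cases are defined as women who enroll prior to the occurrence of the pregnancy outcome", with live birth, miscarriage, stillbirth and termination as the outcomes. An abnormal prenatal finding is not among them. The counterpart is "Retrospective cases are defined as women who enroll or contact the registry after the pregnancy outcome has occurred". The two groups get a separate summary.
- **Measure.** Section 8.7 promises "Summaries of the numbers of pregnancies and incidence proportion (percent) of adverse pregnancy and birth events". Spontaneous abortion belongs to objective 1 and major malformation to objective 2 (section 7).
- **Use.** Section 8.7 allows the results to be set in context with general-population data and with unexposed pregnancies from THAOS.

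On data items, the 8.3 table includes "Date of first day of last menstrual period" and gestational age at exposure. It lists neither gestational age at entry nor prenatal test results known at entry. Table 2 in 8.6.1 already works from a dated receipt ("SRD: Safety Receipt Date"). The limitations in 8.9 are small numbers, missing data and under-reporting.

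**The concern.** Miscarriage risk is concentrated early in pregnancy, and women will enter at different gestational ages. A woman first reported at 16 weeks cannot contribute a loss at 8 weeks, yet she counts in full in the denominator of a crude percentage. A woman who lost her pregnancy at 8 weeks, before anyone reported it, cannot be a prospective case at all. Both effects lower the prospective miscarriage percentage (left truncation).

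Malformations can err the other way. If an abnormal scan or test prompts the report and the pregnancy is still ongoing, the case meets the prospective definition, although the finding drove its selection.

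Both errors depend on when and why reports reach the sponsor. Two populations with the same risks could therefore show different percentages, which weakens the comparison with outside data that 8.7 allows for.

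**Working it through.** The protocol states no expected miscarriage rate, entry-time distribution or sample size, so there is no figure of its own to reproduce. The calculations below are illustrations. All hazards and entry windows are assumptions, and induced abortion is ignored.

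**1. Direction.** Let h_w be the loss hazard in week w, and S_g = product of (1 - h_w) for w = 5 to g - 1, the probability that a pregnancy is still ongoing at week g. Put S_g = S_20 for g ≥ 20.

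- True risk from week 5 to week 20 = 1 - S_20.
- Crude prospective proportion, with intended entry uniform over a set of weeks = Σ(S_g - S_20) / ΣS_g.

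The crude value equals the true risk only if every woman enters at week 5. With any later entry and a positive early hazard it is lower, whatever the shape of the hazard.

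**2. Size under one assumed hazard.** Take 3% per week in weeks 5-8, 1.5% in weeks 9-12 and 0.3% in weeks 13-19.

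- S_9 = 0.97^4 = 0.885
- S_13 = 0.885 × 0.985^4 = 0.833
- S_20 = 0.833 × 0.997^7 = 0.816
- True risk = 1 - 0.816 = 18.4%

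| Entry weeks (uniform) | Σ(S_g - S_20) / ΣS_g | Crude | Entrants before week 20 only |
|---|---|---|---|
| 5-8 | 0.5595 / 3.8236 | 14.6% | 14.6% |
| 6-12 | 0.5738 / 6.2859 | 9.1% | 9.1% |
| 6-20 | 0.6429 / 12.8831 | 5.0% | 5.3% (0.6429 / 12.0671) |
| 8-24 | 0.3641 / 14.2363 | 2.6% | 3.6% (0.3641 / 10.1562) |

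The last column shows that restricting to entry before 20 weeks does little by itself.

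**3. Sensitivity to the hazard.** Take instead hazards that fall by a factor of 0.75 to 0.85 per week, scaled to a chosen true risk. Crude percentages, with ranges over the factor:

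| True risk | Entry 6-12 | Entry 8-16 | Entry 8-30 |
|---|---|---|---|
| 10% | 3.8-5.2 | 1.7-3.0 | 0.7-1.2 |
| 15% | 5.8-8.0 | 2.6-4.6 | 1.1-1.9 |
| 20% | 7.9-10.8 | 3.6-6.3 | 1.5-2.7 |

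**4. What delayed entry recovers.** With true risk 15%, factor 0.80 and entry uniform over weeks 5-30, the expected crude proportion is 2.8%. A Kaplan-Meier estimate in which each woman joins the risk set at her entry week returns 15.0%. It can only estimate risk from the earliest observed entry. Under the step 2 hazards, if nobody enters before week 8, it estimates 1 - 0.816/0.9127 = 10.6%, not 18.4%.

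**5. Pooling with retrospective cases.** With true risk 15%, factor 0.80 and entry over weeks 8-16, the pooled percentage is 3.5% if no earlier loss is reported retrospectively, 9.6% if half are and 15.0% if all are. Preferential reporting of losses from pregnancies that would otherwise go unreported can push it higher still.

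**6. Known-abnormal pregnancies.** Section 6 gives 13 maternal exposures as of 25 September 2019. That is a count of all maternal cases, used here only as a guide to scale. One known-abnormal pregnancy among 13 gives 1/13 = 7.7% (exact 95% CI 0.2% to 36.0%).

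**The case against.** **The study is descriptive, and imprecision swamps the bias.** At 13 pregnancies, 18.4% against 9.1% is about 2.4 against 1.2 losses, and the exact 95% CI for 2/13 runs from 1.9% to 45.4%. This stands as a limit on what any estimator can deliver. It does not excuse the classification, because wide uncertainty around a shifted figure does not cover the shift, and 8.7 itself foresees setting the percentages beside outside data.

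**The protocol already separates prospective from retrospective cases.** It does, and that isolates reporting triggered by the final outcome. Both problems here lie inside the prospective group.

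**Estimators and sub-classification belong in a SAP, and the EDP form is not shown.** Estimator detail can go there. But the protocol itself fixes the entry time, the label and the crude measure. A prenatal result that was never asked for cannot be supplied by a later analysis. Whether the form already asks cannot be checked; the 8.3 table does not list it.

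**Two stronger readings go too far.** A reader might infer that every miscarriage percentage in the study is biased low. The text does not support that: 8.2.1 includes all reported exposures, the percentages in 8.7 are not confined to prospective cases, and step 5 shows that the direction is open once cases are pooled. A reader might also take initial awareness to mean the reporter's awareness, so that someone who knew early but told the sponsor only after a bad outcome would yield a prospective case. The retrospective definition largely answers this, because it covers women who contact the registry after the outcome.

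**Conclusion.** The point holds for the prospective summary. Followed as written, sections 8.1 and 8.7 give a spontaneous-abortion percentage that is too low whenever entry falls after the early weeks of risk. That direction does not rest on the assumed hazards. The size does: in the illustrations the crude figure ranges from about four fifths of the true risk (14.6% against 18.4%) to well under a fifth (2.6% against 18.4%), and the protocol gives no entry times from which to choose.

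The prospective definition also admits pregnancies reported after an abnormal prenatal finding. This can raise the malformation percentage, by 7.7 points for a single case if the denominator is 13. How often it will happen cannot be judged from the document. Neither bias appears in 8.9. Because numbers will be small, the main gain from a change is correct classification and labelling, not a precise risk estimate.

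**What to change.** 1. **8.3 and EDP form:** derive gestational age at the Safety Receipt Date from the last menstrual period, and add one question on prenatal test or scan results known when the pregnancy was reported.
2. **8.7, malformations:** make prospective cases with no known abnormal prenatal finding the main set, and present those with a known finding separately.
3. **8.7, spontaneous abortion:** report it only among prospective pregnancies received before 20 weeks, tabulated by gestational age at receipt. Where numbers allow, put a delayed-entry cumulative incidence beside the crude count, with live birth and induced abortion as competing outcomes, and state the gestational age from which it starts.
4. **8.9:** add late entry and reporting prompted by prenatal findings to the limitations.
5. **8.1, wording only:** tie enrollment to the Safety Receipt Date.

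The cost is one form question and some tabulation; the dates are already held. The delayed-entry estimate will be imprecise at this size and assumes that the timing of entry is unrelated to risk, so it supplements the counts and does not replace them. The 20-week restriction must not stand alone, since it moves the illustrative figures only from 5.0% to 5.3% and from 2.6% to 3.6%.
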